#### **6.4.2.3      Evaluation by 3.0 Tesla MRI (Specific Aim 2)**

**Magnetic Resonance Imaging Procedures** - Participants in this study will undergo 3T MRI at the UPMC Magnetic Resonance Research Center or the Magnetic Resonance Facility, BAMC, Wilford Hall, San Antonio before treatment is initiated and 6 months after injury. Rigorous procedures to ensure high quality MRI that are capable of reliably detecting small changes in muscle structure over time will be undertaken. These include standardized procedures to position and minimize motion of the subject, establishment of criteria to assess the quality of the magnetic resonance images and daily, weekly, monthly and annual quality control procedures for maintenance of the magnetic resonance scanner.

Images of both thighs will be acquired from the ischial tuberosity to just below the knee so that the entire length and volume of the hamstrings will be imaged. A torso coil will be used. Total scan time is approximately 30 minutes. Following a conventional 3-plane localizer, axial, sagittal and coronal T1-weighted non-fat saturated, axial and coronal short inversion recovery time (STIR) and axial and sagittal T2 fat saturated (FS) images will be obtained. The details for each of the sequences are specified in the Table 4 below.

**Table 4 – Summary of MRI Parameters**

Sequence	Slice/Gap Thickness (mm)	Matrix	Field of View
Axial T1 a	8/1	512 x 180	40 cm/phase 75
Sagittal T1 a	5/2	194 x 384	38 cm/phase 84
Coronal T1 a	5/2	192 x 512	40 cm/phase 75
Axial STIR b	8/1	256 x 256	40 cm/phase 75
Axial T2 FS c	8/1	203 x 384	40 cm/phase 75
Sagittal T2 FS c	5/2	194 x 384	38 cm/phase 84
Coronal STIR b	5/2	256 x 256	40 cm/phase 75

a T1 weighted non-fat saturated.  
b Short inversion recovery time.  
c T2 weighted fat saturated.

The primary MRI outcome measures for analysis will be the maximal crano-caudal length and volume of the injury/scar tissue. To calculate volume of injury/scar tissue, the area of injury/scar tissue will be determined on each slice. This area will be multiplied by the slice thickness and summed across all slices in which the injury/scar tissue is visible. Additionally, total volume of the involved compared to the non-involved hamstring muscles will be determined as a measure of muscle atrophy.

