## **2. Clinical Study Objectives:**

### **2.1 Primary objective:**

Our long term objective is to improve muscle healing by decreasing pathologic fibrosis that occurs after skeletal muscle injury limiting effective muscle regeneration. Our **overall hypothesis** is that Losartan, which is an angiotensin II receptor blocker, will improve muscle healing and function after acute hamstring injuries in athletes and military personnel.

In this **phase 1 prospective double-blind placebo-controlled randomized clinical** our objective will be to **evaluate safety and tolerability** and to **provide pilot data** to determine the magnitude of the effect and variability in the outcome of Losartan in comparison to placebo, which will allow a more accurate prediction of sample sized needed for a future definitive trial. The specific aims of the study are to:

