## **6.4.2 Outcome Measures**

The outcomes measures will be collected at the time of study enrolment and at the 1, 2, 3, 4 and 6 weeks and 3, 4, 6, 9 and 12 month follow-up as described in **Table 1** above, using procedures described in a Manual of Operations and Procedures. We will use a **trained** Clinical Research Assistant at each site, who has a background as a physical therapist or athletic trainer, to collect the measures of hamstring flexibility and strength and to conduct all follow-up telephone calls. Prior to data collection, co-I [name] (who has greater than 30 years of experience with collection of clinical outcomes data) will train the Clinical Research Assistants.

A musculoskeletal radiologist will read and interpret the MRI scans to determine the presence and extent of fibrosis and muscle atrophy. A bilateral magnetic resonance imaging (MRI) of both thighs will be conducted. The amount of fibrosis atrophy will be determined from the MRI using MIPAV software (Medical Imaging Processing, Analysis and Visualization, NIH, Bethesda, MD).

All individuals responsible for collecting outcome measures will be blinded to the subject's group assignment throughout the duration of the study.

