**Specific Aim #2: Recovery of Hamstring Muscle Function and Structure**

The primary endpoints to assess hamstring muscle function are the injured to contra-lateral leg differences in the popliteal angle at 6 weeks and 6 months and the injured to contra-lateral ratio of peak isokinetic hamstring torque at 6 weeks and 6 months.

The primary endpoint to assess hamstring structure will be the length and volume of fibrosis within the hamstrings at 6 months as evidence on 3 Tesla MRI.

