### **9.1.2 Secondary endpoints**

#### **Specific Aim #2: Recovery of Hamstring Muscle Function and Structure**

Secondary outcomes for recovery of hamstring muscle function include isometric strength (Newton-meters) of the involved hamstrings expressed as a percentage of strength of the un-injured at 1, 2, 3, 4 and 6 weeks and 6 months. Secondary isokinetic variables that will be explored include the injured to contra-lateral leg ratio of total hamstring work at 60°/sec, involved hamstring to quadriceps ratio in peak torque at 60°/sec, injured to contra-lateral leg ratio of peak torque and total work at 180°/sec and the ratio of work in the last 3 repetitions to work in the first 3 repetitions at 180°/sec at 6 weeks and 6 months.

The secondary outcome for structure of the hamstring will include atrophy of the hamstrings as determined by the ratio of the volume of the injured and contra-lateral leg 6 months after injury.

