## **9.2        Sample size determination**

With an approved sample size of 20 patients (10 in each group), we will not have enough statistical power to detect statistically significant differences in clinical measures between the Losartan and placebo groups. Therefore the objective of this phase 1 trial is to observe trends by group and estimate effect sizes that can be used to inform power calculations in future clinical trials.

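### Scar volume, part of the primary structural endpoint, is computed without the gaps between MRI slices; the series and the tracing rule are not stated

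*Combined protocol and SAP*

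**What the plan says.** Table 4 in section 6.4.2.3 has a column whose heading begins "Slice/Gap Thickness (mm". It lists slice and gap as separate quantities: 8/1 for the three axial series (T1, STIR, T2 FS) and 5/2 for the four others (sagittal T1, coronal T1, sagittal T2 FS, coronal STIR). No series is contiguous.

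The text below the table has the scar area measured on each slice and then says: "This area will be multiplied by the slice thickness and summed across all slices in which the injury/scar tissue is visible". There is no gap term. The section does not say which series is traced or how the outline is drawn on a slice that the lesion only partly fills.

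Section 9.1.1 gives the result primary status for Aim 2: "The primary endpoint to assess hamstring structure will be the length and volume of fibrosis within the hamstrings at 6 months". On method, section 6.4.2 adds only that a musculoskeletal radiologist reads the scans, that "The amount of fibrosis atrophy will be determined from the MRI using MIPAV software", and that outcomes are collected "using procedures described in a Manual of Operations and Procedures". That manual is not among the documents.

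**The concern.** When slices are separated by gaps, each slice stands for its own thickness plus one gap. Multiplying by thickness alone counts only the tissue inside the slices. Table and formula appear together, and the formula does not use the second figure in the table.

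This matters because of what the trial is meant to deliver. Section 2.1 says the pilot is to "determine the magnitude of the effect and variability in the outcome of Losartan in comparison to placebo". Section 9.2 gives up formal power and aims instead to "observe trends by group and estimate effect sizes that can be used to inform power calculations in future clinical trials". For such a trial the scale of the raw estimates is part of the product. Under the formula as written, absolute scar volumes, group differences in volume units and their SDs are not on a true-volume scale. They cannot be set directly beside gap-corrected volumes from another study.

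**Working it through.** **Inputs.** Slice thickness *t* and gap *g* come from Table 4: *t* = 8, *g* = 1 mm (axial); *t* = 5, *g* = 2 mm (sagittal, coronal). The formula is the sum of area × *t* (section 6.4.2.3). The plan states no volume, so there is no figure to reproduce. Assumptions: an ellipsoidal lesion of length *L* across the slices, randomly placed relative to the slice grid. The documents give no lesion lengths.

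**Step 1: traced area is the mean area within the slice.** Slices repeat every *t* + *g*, so the formula averages *V* × *t*/(*t* + *g*), whatever the lesion's shape or length.
- Axial: 8/9 = 0.889, or 11.1% low.
- Sagittal or coronal: 5/7 = 0.714, or 28.6% low.

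Simulation with random slice offsets gave 0.889 and 0.714 at every length tried from 20 to 200 mm.

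**Step 2: traced area is the widest extent visible in the slice (upper bound).** The areas then sum on average to (*V* + *t* × *A*max)/(*t* + *g*). For an ellipsoid *V* = (2/3) × *L* × *A*max, so the ratio to true volume is *t*/(*t* + *g*) × (1 + 1.5*t*/*L*). For axial slices this is 0.889 × (1 + 12/*L*). Replacing thickness by spacing removes the factor 0.889.

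| Axial, ratio to true volume | 40 mm | 80 mm | 160 mm |
|---|---|---|---|
| Mean area, as written (8 mm) | 0.889 | 0.889 | 0.889 |
| Midway, as written | 1.022 | 0.956 | 0.922 |
| Widest extent, as written | 1.156 | 1.022 | 0.956 |
| Mean area, 9 mm spacing | 1.000 | 1.000 | 1.000 |
| Midway, 9 mm spacing | 1.150 | 1.075 | 1.038 |
| Widest extent, 9 mm spacing | 1.300 | 1.150 | 1.075 |

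Simulation (50,000 offsets per setting) gave the same values. Under widest-extent tracing the written formula is right on average only at *L* = 96 mm, where 1 + 12/96 = 9/8. It reads high for shorter lesions and low for longer ones.

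For sagittal or coronal slices at assumed extents of 20, 40 and 60 mm, widest-extent tracing gives 0.982, 0.848 and 0.804 as written, and 1.375, 1.188 and 1.125 with 7 mm spacing.

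**Step 3: what cancels.** With one series, the gap multiplies every volume by the same constant. A standardised difference is (8/9)(*m*1 − *m*2) / ((8/9)*s*), which equals (*m*1 − *m*2)/*s*. Tests, percent change and ratios of volumes are likewise unchanged. A widest-extent bias does not cancel, because it varies with length. A lesion shortening from 80 to 40 mm at the same cross-section loses 50% of its volume, but would read 0.5 × 1.156/1.022 = 0.565 of the starting value, a loss of about 43%.

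**Step 4: an assumed planning use.** Suppose a later trial pairs this pilot's uncorrected axial SD (mean-area tracing) with a target difference in gap-corrected units. The design is a two-sample t test, two-sided 0.05, 80% power.
- True effect 0.5 SD: 64 per arm are needed. The apparent effect is 0.5 × 9/8 = 0.5625, so 51 are planned and actual power is 0.71.
- True effect 0.8 SD: 26 per arm are needed. The apparent effect is 0.9, so 21 are planned and actual power is 0.72.

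If the pilot difference and pilot SD are used together, the sample size does not change.

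**The case against.** The strongest reply is that the consequence is small. A constant 8/9 leaves standardised effect sizes alone, and these are a natural reading of what section 9.2 wants. It also drops out of the secondary outcome, "atrophy of the hamstrings as determined by the ratio of the volume of the injured and contra-lateral leg", and cranio-caudal length does not use the formula. Volumes can be multiplied by 9/8 afterwards. All of this stands, provided one series is used throughout and both the series and the tracing rule are recorded. Nothing in the documents requires that.

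Second, the direction of the error is not established. This also stands: under widest-extent tracing the written formula can read high, and changing to 9 mm spacing alone would then make it worse. Spacing and tracing therefore have to be settled together.

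Third, the manual or the MIPAV spacing setting may already include the gap, or thickness may have been written loosely for spacing. Either is possible. But Table 4 keeps the two quantities apart, so the literal reading is 8 or 5 mm. If the manual differs, the protocol contradicts it on a primary endpoint and needs aligning.

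Fourth, the planning example is hypothetical, since no section proposes such a pairing. That is correct; it shows the mechanism and is not a forecast. The same holds for mixing planes between scans, which under mean-area tracing would make a lesion read 0.714/0.889 = 0.804, or 19.6% lower, on sagittal or coronal slices than on axial ones. Nothing suggests this is intended.

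**Conclusion.** The concern holds. The omission of the gap from the volume formula is certain from section 6.4.2.3. The size and direction of the resulting error are conditional. With mean-area tracing it is 11.1% low on axial series, and 28.6% low only if sagittal or coronal slices are used. With other tracing rules the end-slice overcount can offset or reverse it; those ratios rest on an assumed ellipsoid and assumed lengths.

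The trial's comparisons are not invalidated. What is affected is the absolute scale of scar volume and of its group difference and SD. The formula is wrong as written, the effect is modest, and it should be corrected before scans are read.

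**What to change.** In section 6.4.2.3:

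1. Replace slice thickness in the volume formula with slice spacing, defined as thickness plus gap: 9 mm for axial series, 7 mm for sagittal or coronal.
2. Name one series for volume, the same at both sites and both time points.
3. State how the outline is drawn on partly filled end slices, so that the traced area represents the mean area within the slice. The radiologist should supply a convention that a reader can apply.
4. Confirm that the MIPAV spacing setting and the Manual of Operations and Procedures say the same.

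Items 1 and 3 should be made together, because correcting the spacing alone can increase the error if outlines follow the widest extent. The cost is two or three sentences and a check of one setting and one manual, with no new scans or readers.

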## 6.5 Schedule of activities (Study Table)

**Table 1 – Summary of Study Procedures**

	Pre-treat	Day 0	1w	2w	3w	4w	6w	12w	4m	6m	9m	12m
Informed Consent	X											
Demographic Questionnaire	X											
Activity Level	X		X	X	X	X	X	X	X	X	X	X
Medical History	X											
Vital Signs (standard and orthostatic blood pressure and heart rate)	X		X	X	X	X			X			
Physical Examination	X											

Blood Work	X			X		X	X				
Numerical Pain Rating Scale	X		X	X	X	X	X		X		
Hamstring flexibility	X		X	X	X	X	X		X		
Isometric hamstring strength testing	X		X	X	X	X	X		X		
Isokinetic hamstring strength testing							X		X		
3.0 Tesla MRI	X									X	
Randomization		X									
Day of 1 st Dose		X									
Medication Log Review			X	X	X	X					
Telephone follow-up								X	X	X	X
	Legend: pre-treat = pre-treatment; w = week; m = months										

## 7.

## **Safety and Effectiveness Assessments:**

### **7.2 Safety assessments**

Vital signs (including blood pressure and heart rate) will be monitored daily prior to each rehabilitation session. Blood work, including a chemistry panel with electrolytes and complete blood cell count (CBC) and pregnancy tests for women will be performed prior to randomization and at 2, 4, and 6 weeks after randomization. The blood work will be used to assess hemoglobin and hematocrit counts, serum potassium and uric acid, liver function (alanine aminotransferase (ALT), aspartate aminotransferase (AST) and alkaline phosphatase), renal function (blood urea nitrogen [BUN] and serum creatinine), creatine phosphokinase (CPK) to assess muscle injury, and pregnancy in women (human chorionic gonadotropin (hCG)).

The profile of adverse and serious adverse events will also be monitored to assess safety throughout the duration of the subject's participation in the study.

### **7.2 Effectiveness assessments**

Our overall hypothesis is that Losartan, which is an angiotensin II receptor blocker, will improve muscle healing and function after acute hamstring injuries in athletes and military personnel. The effectiveness assessments for each specific aims of the study are to:

#### **Specific Aim #2: Recovery of Hamstring Muscle Function and Structure.**

Recovery of muscle function will be assessed in terms of hamstring flexibility and strength. Hamstring length will be assessed by measuring the popliteal angle as described by ten Berge et al. To account for variability between subjects, hamstring flexibility will be expressed as the difference in popliteal angle between the hamstring-injured and contra-lateral normal leg. To assess hamstring strength, isometric testing with the knee flexed to 30° and 90° will be performed before treatment and at 1, 2, 3, 4 and 6 weeks and 6 months after enrolment and isokinetic testing at 60° and 180°/sec will be performed 6 weeks and 6 months after enrolment. The detailed procedures for measuring hamstring flexibility and strength are described in section 6.4.2.2.

3 Tesla MRI will be performed at enrolment and at 6 months follow-up to assess hamstring structure in terms of the length and volume of the injury and scarring. Additionally total volume of the injured and contra-lateral hamstrings will be calculated to determine the degree of atrophy. The detailed procedures for use of 3T MRI to assess hamstring structure are described in section 6.4.2.3.

#### **Specific Aim #3: Time to Return to Prior Level of Function**

The primary outcome for return to sports will be the number of days from injury to full, unrestricted return to practice. The secondary outcome for return to sports activity will be the Marx Activity Scale Score at 4 and 6 weeks and 3, 4, 6 and 12 months. At 4 and 6 weeks, the Marx Sports Activity Scale will be modified to measure sports activity in the last week and at 4, 6 and 12 months the scale will be modified to measure sports activity in the past month.

#### **Specific Aim #4: Recurrence of Injury**

Recurrence of injury will be monitored over the course of 12 months after study enrolment and randomization. A subject will be considered to have a recurrent injury if there was a specific mechanism of injury that caused a return of posterior thigh pain, tenderness to palpation along the muscle-tendon unit, pain with resisted knee flexion and the inability to participate in sports activities. Recurrent injuries will be monitored weekly during the course of rehabilitation and at each follow-up study visit (1, 2, 3, 4 & 6 weeks, 6 months) and follow-up phone call (3, 4, 9 and 12 months).

8.

#### **Adverse Event Reporting:**

## 8.1 Adverse event definitions

Adverse event means any untoward medical occurrence associated with the use of the drug in humans, whether or not considered drug related.

Adverse reaction means any adverse event caused by a drug.

Suspected adverse reaction means any adverse event for which there is a reasonable possibility that the drug caused the adverse event. Suspected adverse reaction implies a lesser degree of certainty about causality than “adverse reaction”.

- *Reasonable possibility.* For the purpose of IND safety reporting, “reasonable possibility” means there is evidence to suggest a causal relationship between the drug and the adverse event.

Life-threatening, suspected adverse reaction. A suspected adverse reaction is considered “life-threatening” if, in the view of either the Investigator (i.e., the study site principal investigator) or Sponsor, its occurrence places the patient or research subject at immediate risk of death. It does not include a suspected adverse reaction that had it occurred in a more severe form, might have caused death.

Serious, suspected adverse reaction. A suspected adverse reaction is considered “serious” if, in the view of the Investigator (i.e., the study site principal investigator) or Sponsor, it results in any of the following outcomes: death, a life-threatening adverse reaction, inpatient hospitalization or prolongation of existing hospitalization, a persistent or significant incapacity or substantial disruption of the ability to conduct normal life functions, or a congenital anomaly/birth defect.

- Important drug-related medical events that may not result in death, be life-threatening, or require hospitalization may be considered “serious” when, based upon appropriate medical judgment, they may jeopardize the research subject and may require medical or surgical intervention to prevent one of the outcomes listed in this definition. Examples of such medical events include allergic bronchospasm requiring intensive treatment in the emergency room or at home, blood dyscrasias or convulsions that do not result in inpatient hospitalization, or the development of drug dependency or drug abuse.

Unexpected, suspected adverse reaction. A suspected adverse reaction is considered “unexpected” if it is not listed in the general investigational plan, clinical protocol, or elsewhere in the current IND application; or is not listed at the specificity or severity that has been previously observed and/or specified.

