### **8.2.2.2 Causality and severity assessment**

The Sponsor-Investigator of the IND application will promptly review documented adverse events and abnormal test findings to determine: 1) if the abnormal test finding should be classified as an adverse event; 2) if there is a reasonable possibility that the adverse event was caused by the study drug(s); and 3) if the adverse event meets the criteria for a *serious adverse event*.

If the Sponsor-Investigator's final determination of causality is "unknown and of questionable relationship to the study drug(s)", the adverse event will be classified as *associated with the use of the study drug(s)* for reporting purposes. If the Sponsor-Investigator's final determination of causality is "unknown but not related to the study drug(s)", this determination and the rationale for the determination will be documented in the respective subject's case history.

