The severity of an adverse event will be determined by the study medical director based on the criteria stated in section 8.1. Additionally, the medical director will assign the event a grade of mild, moderate, or severe. If it becomes medically necessary to withdraw the subject from the study, the study medication will be discontinued. The subject will be followed clinically until the adverse event or abnormal test findings felt to be associated with the study drug resolves or stabilizes at a level acceptable to the Sponsor-Investigator. This follow-up will include assessment of vital signs, physical examination and assessment of blood work. Follow-up blood work will be performed 4-6 weeks ( $\pm 3$  days) after discontinuing medication to ensure that lab values have returned to normal ranges after discontinuation of the study medication. The subject will be treated for any medication related problems as clinically appropriate. Information from this appointment will be documented in the subject's case file. The patient will be terminated from the study, and will not complete any further follow-up appointments for the study. Subjects that are terminated from participation in the study due to an adverse event will be replaced by recruitment of another subject.

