## 9.

## **Statistical Methods/Data Analysis:**

### **9.1 Study endpoints**

#### **9.1.1 Primary endpoint(s)**

**Specific Aim #1: To determine safety and tolerability of Losartan when used for treatment of an acute grade II or III hamstring strain.**

To assess safety, vital signs will be monitored daily and we will also monitor the frequency of abnormal lab values as well as adverse and serious adverse events during period of active intervention as well as throughout the subjects' participation in the study. To assess the side effect profile of Losartan in this population, we will monitor the frequency of subject complaints, symptoms (dizziness, new fatigue, peripheral edema, urinary symptoms) and laboratory measures of liver and renal function, haemoglobin and haematocrit counts and serum potassium and uric acid levels. The frequency of abnormal lab values, adverse and serious adverse events and side effects will be monitored separately for the Losartan and placebo control groups.

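### The primary safety endpoint counts serious adverse events, but section 8.1 words its seriousness criteria only for suspected or drug-related events, in conflict with 8.2.2, 8.2.2.2 and 8.3.2

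*Combined protocol and SAP*

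**What the plan says.** **What is counted.** Section 9.1.1, under Specific Aim #1, monitors the "frequency of abnormal lab values as well as adverse and serious adverse events during period of active intervention" and over the rest of each subject's participation, separately by group. Section 9.5 repeats this and compares the groups with Fisher exact tests. Neither section limits the serious events to drug-related ones.

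**What counts as serious.** Section 8.1 defines an adverse event without a causality condition: "any untoward medical occurrence associated with the use of the drug in humans, whether or not considered drug related". It then sets a narrower class: "Suspected adverse reaction means any adverse event for which there is a reasonable possibility that the drug caused the adverse event". Seriousness is defined only for that class, in the definition that opens "Serious, suspected adverse reaction. A suspected adverse reaction is considered" serious. The extension for other medically important events is also causal: "Important drug-related medical events that may not result in death, be life-threatening, or require hospitalization may be considered" serious. There is no separate definition of a serious adverse event.

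**Who decides.** In 8.1 a reaction is serious if, "in the view of the Investigator (i.e., the study site principal investigator) or Sponsor, it results in any of the following outcomes". In 8.2.2.2, "The Sponsor-Investigator of the IND application will promptly review documented adverse events and abnormal test findings to determine" three things: whether a test finding is an adverse event, whether the drug may have caused the event, and whether the event is serious. In 8.4, "The severity of an adverse event will be determined by the study medical director based on the criteria stated in section 8.1".

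**The concern.** In a randomised, blinded comparison the cleanest safety contrast counts every serious event in each arm, whatever anyone thinks caused it. Randomisation can then reveal a harm that nobody suspected. A case-by-case opinion on cause tends to keep events that resemble known drug effects and to drop the rest.

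Safety and tolerability is Specific Aim #1, and there are 10 subjects per arm. Serious events will be few, so how one event is classified can visibly change the table. Two sites holding the same protocol could classify the same hospitalisation differently: one by the heading in 8.1, the other by the separate steps in 8.2.2.2.

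**Working it through.** The plan states no serious-event rate, alpha or power for this endpoint, so there is no figure to reproduce. The check is mainly of the text.

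**1. Is seriousness tied to causality?**

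| Section | Treatment of seriousness |
|---|---|
| 8.1 | Defined for suspected reactions; important events must be drug-related |
| 8.2.2 | All events recorded whatever the suspected cause; seriousness and causality listed as two tasks |
| 8.2.2.2 | Causality is item 2, seriousness is item 3; item 3 applies to the adverse event |
| 8.3.2 | Associated with the drug, serious and unexpected are three separate conditions |
| 9.1.1, 9.5 | Serious adverse events counted by arm, no causality limit |

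Sections 8.2.2, 8.2.2.2 and 8.3.2 point to a causality-free classification. Section 8.2.2.2 nevertheless refers to criteria for a serious adverse event, and the only ones written are in 8.1.

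**2. Does a generous reading of 8.1 remove the problem?** Suppose the reader ignores the word suspected and applies the listed outcomes to any adverse event. Two criteria still carry a causal test. The life-threatening outcome is worded as an adverse reaction, which 8.1 defines as an event caused by a drug. The important-event clause requires a drug-related event.

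| Event judged unrelated | 8.1 literally | Listed outcomes applied to any event | Cause-free definition |
|---|---|---|---|
| Hospitalisation | not serious | serious | serious |
| Life-threatening, no other listed outcome | not serious | not serious | serious |
| Important medical event, no listed outcome | not serious | not serious | serious |

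The generous reading resolves only the first row.

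**3. Who classifies?** 8.1 names the site principal investigator or the Sponsor; 8.2.2.2 names the Sponsor-Investigator; 8.4 names the medical director, for severity by the 8.1 criteria. Section 8.1 has no severity scale, and 8.4 adds the mild, moderate or severe grade as a further step. What the 8.4 reference to 8.1 means is therefore unclear.

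**4. Illustration of size.** Let p be the proportion of the 20 subjects with a serious event (at most one each) and a the fraction of such events judged possibly drug-related. Both are assumptions. If 8.1 were applied literally every time, the probability of a table with no serious event although at least one occurred is (1 − pa)^20 − (1 − p)^20.

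| p | a = 0.2 | a = 0.5 |
|---|---|---|
| 0.01 | 0.961 − 0.818 = 0.14 | 0.905 − 0.818 = 0.09 |
| 0.02 | 0.923 − 0.668 = 0.26 | 0.818 − 0.668 = 0.15 |
| 0.05 | 0.818 − 0.358 = 0.46 | 0.603 − 0.358 = 0.24 |
| 0.10 | 0.668 − 0.122 = 0.55 | 0.358 − 0.122 = 0.24 |

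For the Fisher test with 10 per arm (two-sided), 5 v 0 subjects gives p = 0.033 and 4 v 0 gives p = 0.087, so one reclassified event can cross 0.05. With p = 0.05 to 0.10, however, only 20 × 0.05 = 1 to 20 × 0.10 = 2 subjects are expected to have a serious event. The practical effect is on the descriptive table more than on the test.

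**The case against.** The strongest reply is that the plan intends a cause-free count. Recording in 8.2.2 ignores suspected cause, 8.2.2.2 judges seriousness separately from causality, and the first condition in 8.3.2 would be redundant if serious already implied drug-related. The wording in 8.1 matches the FDA reporting trigger in 8.3.1.1, where a causal condition belongs. A reader might infer from 8.1 that the by-arm comparison is in fact filtered by causality opinion; the documents do not support that. The point stands as a conflict, because the endpoint still depends on criteria found only in 8.1.

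A reader might also infer that unsuspected harms would be lost. They would not be. An unrelated hospitalisation stays in the case history and in the all-adverse-event comparison, and only its serious label is at risk.

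Nor does the definition put expedited reports at risk. The reports in 8.3 are limited to suspected or associated events in any case.

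On the deciders, it is tempting to say that a site's classification can be overruled. No section describes downgrading, and the final determination in 8.2.2.2 concerns causality. Sponsor and Sponsor-Investigator overlap, and 8.4 speaks of severity. What remains is whether the site investigator's view alone suffices, and what the reference in 8.4 to 8.1 means.

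The illustrated probabilities are easily overstated. Subjects are active, aged 18 to 35 and free of major co-morbidity, so the lower rates are plausible. Section 8.2.2.2 also treats events of questionable relationship as associated with the drug for reporting, which leans towards attribution.

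**Conclusion.** The concern holds as a definitional conflict in the primary safety endpoint. Serious adverse events are counted by arm, but their only written criteria depend on causality, while 8.2.2, 8.2.2.2 and 8.3.2 treat the two judgements as distinct. Followed literally, 8.1 removes unrelated serious events from the serious-event count but not from the all-adverse-event count. Even a generous reading leaves a causal test in the life-threatening and important-event criteria.

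The size cannot be derived from the documents. The range of about 9% to 55% is an illustration that needs assumed event and attribution rates, and literal use of 8.1 for every event. It is not an estimate of what will happen. The classifying role is inconsistent enough to need reconciling, but it is not an established conflict over who prevails. The change is worth making because the serious-event table is a central safety output of a small trial and the correction is only wording.

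**What to change.** - **8.1:** Define a serious adverse event as any adverse event, whatever its suspected cause, that meets the listed outcomes or is an important medical event. Remove the causal wording from the life-threatening and important-event criteria. Keep the serious suspected adverse reaction as a separate term for reporting.
- **9.1.1 and 9.5:** State that all serious adverse events are counted by arm regardless of causality.
- **8.3:** Leave the causality condition as it is for the FDA and IRB reports.
- **8.1, 8.2.2.2 and 8.4:** State one rule for who classifies seriousness and what happens if the site and the Sponsor-Investigator differ. In 8.4, separate seriousness from the mild, moderate or severe grade, and correct the reference to 8.1 for severity.

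The cost is wording in five sections. No new data are needed, because 8.2.2 already records every event. The small downside is that the serious-event table may look slightly less favourable.
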